2.4 STUDY ENDPOINTS

Overall, study endpoints pre- and post- nitrites will include:

1. Skeletal muscle bioenergetics: Mitochondrial function will be assessed using respirometry. Polymerase chain reaction (PCR) to assess pertinent gene expression (ubiquitin [MuRF, Atrogin1, FoxO], FNDC5, PGC1 α , Sirtuin 3).
2. Serology: plasma BNP, inflammatory markers, plasma nitrite and platelet bioenergetics (using Seahorse XF analysis) (40), i.e., including glycolytic as well as basal and maximal respiratory rates.
3. Measures of physical function will include CPX indices, gait speed, strength (endurance, power), and balance.
4. Quality of life: Kansas City Cardiomyopathy Questionnaire.

2.5 STATISTICAL ANALYSIS

Sample Size Justification: We believe our proposed sample size is adequate for successfully addressing the aims of this initial investigation. Numerous published pilot studies leading to subsequent successful larger trials have used similar sample sizes (47, 48). Our prior data indicate between-subject standard deviation of approximately 32 pmol O₂/min/10⁶ cells in platelet mitochondrial respiration rate change subsequent to administration of nitrite (49). Based on this estimate, with the proposed sample sizes, we will be able to detect statistical significance of a within-group change as small as 32 pmol O₂/min/10⁶ cells, and a between-group difference as small as 42 pmol O₂/min/10⁶ cells with 80% statistical power in two-tailed tests conducted at $\alpha=0.05$. These correspond to large effect sizes by Cohen's *d* criteria (50), and thus afford an adequate level of statistical sensitivity in our pilot investigation.

Data Analysis: Our analytic strategy will involve formal statistical analyses, but in our interpretation, we will also pay attention to descriptive statistics, graphical summarizations of individual participant data such as needle plots (51,52), and magnitudes of parameter estimates from modeling in addition to their statistical significance based on *p*-values and a strict criterion based on $\alpha=0.05$. Such an interpretive strategy is appropriate in an initial study such as ours, where the cost of a missed finding is far greater than a false finding. We will fit a series of linear mixed models using the SAS[®] MIXED procedure (SAS Institute, Inc., Cary, North Carolina) with each of the skeletal muscle, platelet, gene expression, inflammatory, oxygen uptake and physical function related measures as the dependent variable; participant group (HF_rEF/HF_pEF/control), time point (baseline/4-week) and their interaction as fixed effects of interest; and a participant random effect to account for multiple measurements from the same participants. We will appropriately create means contrasts to estimate (a) between time changes in each of the groups corresponding to periods of usual care and nitrite usage, and (b) compare the said changes across the three groups. We will use Pearson/Spearman correlations to quantify strength of associations between changes in measures of skeletal physiology and those of strength, gait speed and balance. Finally, in addition to drawing preliminary conclusions, we will use our descriptive statistics for formal sample size computations in planning a larger subsequent trial to more definitively examine the impact of nitrites.

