
Study Design:
	
The study aims to assess the safety and feasibility of oral nitrite in adults with HFrEF, HFpEF or healthy control.
 
Subjects who meet the Inclusion Criteria and none of the Exclusion Criteria will receive oral sodium nitrite for 4 weeks. We will stratify dosing as below:
 
Study drug to be initiated and prescribed as below:
 
 a. 20 mg tid to subjects who 
 i. are \geq80 years of age or, ii. are age 70 to <80 years with recent history of low blood pressure or other factors that PI judges to be at higher risk for hypotensive response b. 40 mg tid to subjects who 
 i. are age 70 to <80 with no recent history of low blood pressures or PI judges to be at lower risk for hypotensive response c. Subjects to ingest drug once in the morning and again in the early afternoon and again in the evening, approximately 6 hours apart.

	
Subjects will be evaluated as outpatients with the first dose of study drug. Blood pressure, heart rate, methemoglobin levels and plasma nitrite will be measured in the first two hours after dosing. Every week safety visits will occur by phone to assess symptoms, adverse events (AE), interval histories and medication compliance review.
 
Subjects will also be contacted by the study investigator and/or the study coordinator by phone for a follow-up assessment one week following completion of Visit 5.

Planned Sample Size:	30 subjects
Duration of Treatment:	4 weeks

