Chronic dietary supplementation of inorganic sodium nitrate in obese, hypertensive, insulin resistant mice lacking the gene for endothelial NO synthase (eNOS) (20) was studied. With a 10 week treatment of a modest dose of sodium nitrate of 0.1 mmol/kg/day (8.5 mg/kg/day) in the drinking water, significant reductions in blood pressure, fasting blood glucose, HbA1C, and proinsulin to insulin ratio were demonstrated, indicating reduced demands on the β -cell for insulin secretion.

Sodium nitrate drug is considered a source of nitrite through salivary nitrate reduction. Despite the plasma nitrite rise following a single oral sodium nitrate dose, Drs. [name], [name] and [name] recently demonstrated in a phase I PK/PD study in 10 normal volunteers that no persistent blood pressure reduction with sodium nitrate 1,000 mg. In contrast, in the same phase I PK/PD study in

10 normal volunteers, they showed blood pressure decline in systolic, diastolic and mean arterial pressures over 3 hours with sodium nitrite 20 mg. The oral sodium nitrite half-life was about 40-minutes and the effects of nitrite only lasted ≤ 6 hours. This was demonstrated by the plasma nitrite levels returning to baseline levels between 3 and 6 hours after nitrite dosing (i.e. the drug was given and gone out of the circulation within 6 hours). Specifically, mean baseline (pre-nitrite dosing) blood nitrite concentrations were 0.129 micromolar with a peak at 30 minutes of 5.5 micromolar, and return to baseline levels between the 3- (0.176 micromolar) and 6-hour (0.103 micromolar) monitoring time points. In addition, there were no serious adverse events when these normotensive individuals received sodium nitrite.

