2.2.5. Medication Compliance

Subjects will self-administer their first dose of study medication under the supervision of the CTRC nurse (physician investigator will be immediately available) in the outpatient CTRC during Visit 3, following completion of all baseline clinic assessments. Subjects will also be dispensed their study medication (42-day supply) for home use, including four 7-day prefilled and labelled pill boxes and drug/symptom diary cards to help with compliance and to help reduce burden or confusion. (Visit 4 may be scheduled up to and on the 42nd day from visit 3 (25-35±5 days); additional drug will be distributed with the initial dispensation if needed to meet the need.) Subjects will return the previously dispensed study medication when they return for Visit 4 approximately 4 weeks later (+1 week if need be for flexibility of scheduling) and medication compliance will be assessed. The study coordinator will review the daily diary card with each phone call evaluation and also assess medication compliance with queries regarding empty pill compartments in the current 7-day box and remaining boxes. In the event that the compliance rate is <80% (subjects' report of doses taken/total doses prescribed at that date & time *100), subjects will be re-educated on medication compliance. If medication compliance repeatedly falls outside of the acceptable range, the study investigators will discuss subject eligibility for continued participation in the study.

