- Blood sampling via IV line to include: research blood for inflammatory peptides (IL-1, IL-6, IL-15, TNF α), platelet sample and nitrite levels. Blood samples will be drawn into a 1) heparinized syringe (baseline and approximately 30 mins. and 2 hours post study drug administration) and 2) a cell preparation tube (CPT) (baseline and approximately 30 mins and 2 hours post study drug administration). Heparinized blood will be immediately centrifuged at bedside to separate plasma and the plasma and red cells separately flash frozen for later nitrite measurements (via reductive chemiluminescence to determine that nitrite levels were increased in the muscle as described. The second tube of blood (CPT tube) will be immediately subjected to differential centrifugation in order to isolate platelets. Platelets will then be subjected to Seahorse extracellular flux analysis in order to measure bioenergetic profile including basal, non-ATP producing, maximal and non-mitochondrial respiratory rates along with glycolytic rate. Extra aliquots will be stored for use in future studies. Two 10 ml purple top and 2 10 ml red top tubes will be used to collect blood for inflammatory peptides. Total volume of blood drawn will be 88 ml (6 tablespoons).

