- The Kansas City Cardiomyopathy Questionnaire will be used to measure disease-specific health-related quality of life (QOL). This 24-item instrument produces the following scores: Physical Limitation, Symptoms, Symptom Stability, Social Limitation, Self-efficacy, Quality of Life, and two summary measures, and is widely used as a standard by which quality of life, self-efficacy, and other personal perspectives related to functional capacity at baseline and over time. Subjects in the healthy elderly control group will be asked to complete the SF-12.
- 24-hour Dietary recall. The study coordinator will collect a post 24-hour recall of all foods eaten from subjects for analysis for calories, macronutrients, sodium, nitrates and nitrites.

Visit 5 (Final Completion Visit - 2-7 \pm 7 days following Visit 4)

Subjects will be fasting and take their last dose of study drug at home on their usual schedule prior to scheduled testing time. Upon arrival to the CTRC, subjects will be served a standardized breakfast as described in visit 3, then interval history and brief physical exam; temperature, blood pressure, pulse oximetry for methemoglobin %, breathing rate, heart rate and body weight will be documented; additionally, AE and symptom assessment, medication compliance via drug diary cards and pill boxes, and confirmation of last dose will be performed prior to assessment procedures. Prior to the biopsy, study staff will call indicated subjects to hold their anti-platelet and anti-coagulation medications for 1-5 days (depending on the different medications and relative half-lives). This visit will last approximately 2 hours.

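### Section 2.5 gives the timed post-dose nitrite and platelet samples no formal analysis, omits plasma nitrite from the model, and leaves a platelet contrast that mixes 4 weeks of treatment with the latest dose

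*Combined protocol and SAP*

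**What the plan says.** **Sampling at Visit 3 (section 2.3.1).** Plasma for nitrite goes into a "heparinized syringe (baseline and approximately 30 mins. and 2 hours post study drug administration"), and platelets into "a cell preparation tube (CPT) (baseline and approximately 30 mins and 2 hours post study drug administration"). The dose is observed: "Subjects will self-administer their first dose of study medication under the supervision of the CTRC nurse" (section 2.2.5). The Study Design entry of the synopsis also says that "methemoglobin levels and plasma nitrite will be measured in the first two hours after dosing".

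**Sampling at Visit 5 (section 2.3.1).** There is one draw for nitrite and one for platelets. Subjects are to "take their last dose of study drug at home on their usual schedule prior to scheduled testing time". On arrival they eat a standardized breakfast and go through history, examination and compliance checks. No interval from dose to blood draw is set.

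**Analysis (section 2.5, Data Analysis).** The linear mixed model takes the "skeletal muscle, platelet, gene expression, inflammatory, oxygen uptake and physical function related measures as the dependent variable". Its fixed effects are group, "time point (baseline/4-week) and their interaction as fixed effects of interest". Correlations are planned between changes in skeletal physiology and strength, gait speed and balance; none involves plasma nitrite.

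**Aims and endpoints (sections 1.2 and 2.4).** Aim 2 is to show that plasma nitrite rises. Aim 3 links that rise to muscle and platelet metabolism. Both plasma nitrite and platelet bioenergetics are listed endpoints.

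**The concern.** Two gaps meet here. First, Aim 2 has no named test: nitrite is missing from the model, and the samples with a known dose and a known time have no formal analysis. Second, platelet respiration, the only outcome with a power calculation, is compared between a drug-free sample and one taken after a recent dose. A difference could reflect 4 weeks of treatment, the latest dose, or both. The Visit 3 post-dose samples are the only data in the study that show what a single dose does to platelets, and the model has no time level for them.

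At stake is how the main mechanistic result is read, and whether a larger trial is planned on a 4-week effect that may partly be a short-lived dose effect.

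**Working it through.** **1. The plan's own power figures.** Inputs from section 2.5: SD of platelet change 32, two-sided alpha 0.05, power 80%. Assumption: 10 per group, since the documents give 30 in three groups and no split. With the noncentral t distribution:
- within group, paired t on 9 df: detectable change 31.9 (plan: 32)
- between groups, two-sample t on 18 df: detectable difference 42.4 (plan: 42); pooled over three groups, 27 df: 41.6

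Both figures reproduce, so the point does not rest on a sample-size error. The plan does not say at what time after dosing the SD of 32 was observed, so it is unclear whether the figures describe an acute or a 4-week change.

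**2. Measurements without a specified analysis.** 30 subjects × 2 post-dose times × 2 assays = 120 planned measurements, if every subject gives every sample.

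**3. How far Visit 5 nitrite depends on time since dose.** Section 2.2.2 gives, for 20 mg in normal volunteers, a baseline of 0.129 micromolar "with a peak at 30 minutes of 5.5 micromolar", then 0.176 at 3 hours and 0.103 at 6 hours, with a half-life of about 40 minutes. As ratios to baseline: 5.5/0.129 = 42.6; 0.176/0.129 = 1.36; 0.103/0.129 = 0.80.

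Between the reported points, take a single exponential decline from the peak:

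level(t) = 0.129 + (5.5 − 0.129) × 2^(−(t − 0.5)/h), with t in hours since dose and h the half-life in hours.

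The stated half-life gives h = 40/60. The reported 3-hour value implies a faster fall: h = 2.5 × ln 2 / ln(5.371/0.047) = 0.366 hours, about 22 minutes.

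| Time since dose | h from the 3-hour value (22 min) | h as stated (40 min) |
|---|---|---|
| 1 h | 17-fold | 26-fold |
| 2 h | 3.4-fold | 9.8-fold |
| 3 h | 1.4-fold | 4.1-fold |

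A delay of 1 hour rather than 3 changes the expected Visit 5 nitrite by a factor of about 6 (26/4.1) to 12 (17/1.4).

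**4. What the platelet contrast estimates.** Let a be the acute effect of a dose, c any lasting effect of 4 weeks, and f the fraction of a still present at the Visit 5 draw. Then Visit 5 minus Visit 3 pre-dose = c + f × a. With f = 1, the pairs (a, c) = (32, 0), (20, 12) and (0, 32) all give 32. With f = 0.5 they give 16, 22 and 32. The contrast alone cannot tell these apart. The Visit 3 post-dose samples estimate a at two known times; f stays unknown without the dosing time and a model for the decline.

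**5. Precision after the change.** If the SD of each change is 32 (assumption), any one platelet contrast at 10 per group, on 27 df, has a detectable change of 29.4 within group and 41.6 between groups. The 30-minute change averaged over all 30 subjects has 17.0. Nothing is lost by adding time levels.

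**The case against.** **The samples are not shown to be discarded.** A reader might infer that they are thrown away. The documents do not say so. Section 2.5 also promises descriptive statistics and individual plots, with real weight in interpretation, and these could include the post-dose values. Table 1 lists the two-hour draws as safety sampling, so they have a safety purpose too. This stands: the supportable statement is that no formal analysis is specified. But section 2.3.1 sends the same samples for nitrite and Seahorse assay, which are endpoints, so safety is not their only role.

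**No nitrite contrast is stated.** A reader might also infer that the plan tests nitrite by a 4-week contrast that could come out near zero. Nitrite is not a listed dependent variable, so there is no such contrast. A Visit 5 level close to baseline would also need roughly 3 hours or more since the dose, and no interval is given.

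**Dosing time can be recovered.** Subjects record dosing times on diary cards (section 2.2), and Visit 5 reviews the cards and confirms the last dose. This is a fair point, and the fix uses it. Section 2.5 does not yet bring that information into the analysis.

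**A first-dose rise largely repeats what is known.** The volunteer study already showed it, and Aim 3 needs the Visit 5 nitrite, which pairs with treated muscle. Both are right. Hence Visit 5 nitrite should be kept for Aim 3, and the timed contrast used for Aim 2 in this older population.

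**The split is incomplete.** This also stands. It is tempting to accept a 4-week platelet effect only when the total change exceeds the acute change. That rule is not valid: it compares fixed post-dose times with a variable lag, the dose may have been lowered in between (section 2.2.6), and a real sustained effect smaller than the acute peak would be rejected.

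**Conclusion.** The point holds as a gap in the specified analysis, and it is worth correcting even in a pilot. Aim 2 has no named test, and the platelet change in the stated model is the combined effect of 4 weeks of treatment and the most recent dose.

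The size for nitrite is the range in the table. It assumes that the 20 mg volunteer kinetics carry over to older patients with heart failure and to 40 mg, and that the decline is roughly exponential. For platelets no size can be given, because the documents hold no data on how fast an acute platelet effect fades. The argument also takes the Visit 5 home dose to be that morning's, the natural reading of a fasting visit with breakfast on arrival.

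The documents do not support saying that the 4-week platelet change is only an acute effect. Nor would the Visit 3 samples separate the two fully: the acute change follows the biopsy, has no control, and rests on a first dose. Muscle is outside this remedy altogether, being sampled only before the first dose and at Visit 5.

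**What to change.** In section 2.5:

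1. Add plasma nitrite, on the log scale, as a dependent variable.
2. For nitrite and platelet measures, replace the two time levels by four: Visit 3 pre-dose, 30 minutes, 2 hours, and Visit 5. Use an unstructured or time-heterogeneous covariance, because a participant random effect alone assumes equal variance at peak and at baseline.
3. Prespecify 30 minutes minus pre-dose as the timed test of Aim 2. Keep Visit 5 nitrite for the association with treated muscle in Aim 3.
4. Report the acute platelet change (Visit 3 post-dose minus pre-dose) and the total change (Visit 5 minus Visit 3 pre-dose) side by side, with no rule that one must exceed the other.
5. Take time since last dose at Visit 5 from the diary and the last-dose confirmation, and report it or adjust for it.
6. Describe the total platelet change as the combined effect of 4 weeks of treatment and the most recent dose, and state the limits of the acute comparison given above.
7. Say which time after dosing the SD of 32 refers to.

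Cost: revised wording, a little more programming, and a few more contrasts to interpret. The protocol already provides for the samples and the diary, so no patients, visits or blood are added.

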1.2 SPECIFIC AIMS

Hypothesis:

Oral supplementation with nitrite will intrinsically improve skeletal muscle performance in HF as a vital means to improve physical function and moderate effects of disease itself as well as well as to frailties and enfeeblements associated with the disease. This will potentially improve efficacy and quality of care, and also potentially mitigate the skyrocketing costs associated with aggregate HF management.

Specific Aims:

Aim 1: To demonstrate that oral nitrite pills provide skeletal muscle physiological benefit in old HFrEF and HFpEF patients

Aim 2: To show that oral supplements are manifest as increased plasma nitrite.

Aim 3: To show that increased plasma nitrite is associated with improved skeletal muscle (mitochondrial respirometry) and platelet (Seahorse XF) metabolism.

Aim 4: To demonstrate that improved metabolism is associated with shifts in skeletal muscle anabolic gene expression (FNDC5, PGC1 α , Sirtuin 3) as well as reduced catabolic gene expression (ubiquitin [MuRF, Atrogin1]) and inflammation (TNF α , IL-1 β , IL-6).

Aim 5: To demonstrate that improved skeletal physiology achieved using oral nitrite pills is associated with improved clinical indices in old HFrEF and HFpEF patients:

Aim 6: To show that oral nitrite supplements increase efficiency of work, i.e., reduced oxygen uptake (VO₂) required for the same work intensity.

BACKGROUND

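### The hypothesis concerns heart failure as a whole, but section 2.5 names no contrast for the average HF change or for HF against control; two added contrasts in the planned model would supply both.

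*Combined protocol and SAP*

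**What the plan says.** Section 1.2 (repeated in the synopsis) states one hypothesis for one disease population: "Oral supplementation with nitrite will intrinsically improve skeletal muscle performance in HF". Aims 1 and 5 each name HFrEF and HFpEF patients together.

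Section 2.5, Data Analysis, fits a linear mixed model to each outcome. The fixed effects are group (three levels: HFrEF, HFpEF, control), time (baseline, 4 weeks) and their interaction, with a random participant effect. Two sets of contrasts are named. Set (a) estimates "between time changes in each of the groups". Set (b) will "compare the said changes across the three groups".

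The sample size paragraph of section 2.5 likewise gives only two figures, a "within-group change as small as 32 pmol" and "a between-group difference as small as 42 pmol", both for platelet mitochondrial respiration. No section mentions a combined HF estimate or a contrast of HF with control.

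**The concern.** The study asks whether nitrite helps older HF patients, but the named contrasts answer that only separately for each HF type, in groups of about 10. A reader who wants the HF effect must combine two estimates informally or choose a pooling rule after seeing the data.

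Two things are at stake. The first is precision: averaging the two HF changes uses about 20 participants instead of 10, which shrinks the standard error by a factor of 1/√2. The second is interpretation. If both types truly change by the same moderate amount, two tests at about 50% power each will often disagree by chance, and one significant result beside one non-significant result can be taken for a difference between HF types. Section 2.5 itself says a missed finding costs this study more than a false one, and that the results will be used to size a larger trial.

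**Working it through.** **Inputs.** From section 2.5: "Our prior data indicate between-subject standard deviation of approximately 32 pmol" for the change, so SD = 32; 80% power; two-sided α = 0.05. From the synopsis and section 2.1: 30 participants in three groups. The split is not stated. I assume 10/10/10, which reproduces both of the plan's figures and fits the 10 controls mentioned in section 2.2.2. I also assume all are evaluable and the SD is the same in each group. Power is from the noncentral t distribution; the detectable change is the value giving 80% power.

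**Step 1: the plan's own figures.**
- Within one group: SE = 32/√10 = 10.12, df = 10 − 1 = 9. Detectable change 31.9 (stated 32; power at 32 is 80.3%).
- Between two groups: SE = 32 × √(2/10) = 14.31, df = 18. Detectable difference 42.4 (stated 42; power at 42 is 79.3%).

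Both are reproduced, so the stated figures are correct for separate t-tests with 10 per group.

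**Step 2: degrees of freedom of the planned model.** With two time points and complete data, the changes are estimated with a common variance on 30 − 3 = 27 df. On that basis one group has a detectable change of 29.4, and two groups of 10 a detectable difference of 41.6.

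**Step 3: the contrasts not named.**
- Mean HF change = (HFrEF change + HFpEF change)/2. SE = ½ × √(32²/10 + 32²/10) = 32/√20 = 7.16.
- That mean minus the control change. SE = 32 × √(1/20 + 1/10) = 12.39.

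| Quantity | Separate t-tests | Model, 27 df |
|---|---|---|
| Detectable change, one HF group (n = 10) | 31.9 (9 df) | 29.4 |
| Detectable change, HF mean (n = 20) | 21.2 (18 df) | 20.8 |
| Detectable difference, one HF group v control | 42.4 (18 df) | 41.6 |
| Detectable difference, HF mean v control | 36.0 (28 df) | 36.0 |
| 95% CI half-width, one HF group | 22.9 | 20.8 |
| 95% CI half-width, HF mean | 15.0 | 14.7 |

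On the model's df the detectable HF change falls by 1 − 20.8/29.4 = 29%, and the HF-v-control difference by 1 − 36.0/41.6 = 13%.

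**Step 4: both HF types truly change by 21.** Power in one group is 46% (9 df) or 52% (27 df); for the HF mean it is 79% (18 df) or 81% (27 df). Treating the two group tests as independent, on 9 df:
- both miss: 0.54² = 29% (23% on 27 df);
- both significant: 0.46² = 21%;
- exactly one significant: 2 × 0.46 × 0.54 = 50%.

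**Step 5: only one HF type responds, by 32.** The HF mean change is 32/2 = 16. Power of the pooled contrast is 56% (18 df) or 58% (27 df), against 80% (9 df) or 86% (27 df) for the responding group alone.

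**Step 6: fewer evaluable HF participants.** Treating the HF participants as one sample (n − 1 df), the pooled detectable change is 21.1 with 20, 22.4 with 18, 24.0 with 16 and 25.9 with 14.

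**The case against.** The strongest reply is that separate estimates are a reasonable target here. Section 2.1 defines three groups, section 1.3 describes muscle changes in HFpEF as historically less clear than in HFrEF, and section 1.4 says only that both types may benefit in theory. The blood pressure observations in section 2.2.2 cover three HF patients and say nothing about muscle. If the types differ, pooling dilutes the effect, as step 5 shows. This stands: it rules out replacing the group estimates, and it makes promoting the pooled mean to the leading test a matter of judgement. It is no argument against reporting the pooled contrast beside them.

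Three stronger readings are tempting, and the documents do not support them.

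- A reader might infer that half the HF sample is given up. It is not: all participants enter one model and both HF estimates are reported.
- A reader might infer that a real HF effect would probably be missed in both groups. At a true change of 21 that probability is 23–29%. The likelier outcome is a split result, about half the time.
- A reader might infer that non-significant group results would be read as no effect. Section 2.5 says the size of estimates, descriptive statistics and individual plots will be weighed with p-values, so that does not follow.

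It is also fair to say that set (b) already compares groups and that its general wording does not exclude an HF-versus-control contrast. But the contrast is not named, so it is not prespecified.

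**Conclusion.** The point holds as a gap in the contrasts named, not as an error in the model or in the stated 32 and 42. The quantity in the hypothesis, the change in HF, has no planned estimate, and the planned model could give one with a detectable change of about 21 instead of about 29 (32 by separate t-test). HF against control would improve from about 42 to about 36.

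These figures are conditional on an inferred 10/10/10 split, full evaluability and equal SDs; the power figures at 21 also need both HF types to change by that amount. They apply to platelet respiration only, the one outcome with a stated SD, and that SD is referenced to a personal communication. The hypothesis itself concerns skeletal muscle, for which no SD is given. The ratio of about 1/√2 in the standard error applies to any outcome with equal group sizes and equal SDs; the absolute figures do not carry over. This is a worthwhile, inexpensive improvement; leaving it out would not invalidate the study.

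**What to change.** In section 2.5, Data Analysis, prespecify two further contrasts from the planned mixed model for each outcome:

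1. the equally weighted mean of the HFrEF and HFpEF changes from baseline to 4 weeks;
2. that mean minus the control change.

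State that they are reported alongside, not in place of, the change in each group and the HFrEF-versus-HFpEF difference in change, so that disagreement between the HF types stays visible. For quality of life, HF participants complete the KCCQ and controls the SF-12, so contrast 2 does not apply there.

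If the detectable HF change of about 21 is added to the sample size paragraph, give its conditions with it: platelet respiration, SD of change 32, 10 evaluable per group, equal SDs.

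The cost is two ESTIMATE statements per model and two or three sentences, with no change to sample size, visits or treatment. The downside is that the pooled figure averages two HF types and is weaker if only one responds (about 58% power against 80–86% in the responding group, for a change of 32 in one type), which is why the separate estimates must be kept.

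### Section 2.5 plans no association analysis for Aims 3 and 4, and its Aim 5 correlations state neither an analysis set nor any account of group

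*Combined protocol and SAP*

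**What the plan says.** Section 1.2 words Aims 3, 4 and 5 as associations. Aim 3 is "To show that increased plasma nitrite is associated with improved skeletal muscle (mitochondrial respirometry) and platelet (Seahorse XF) metabolism". Aim 4 is that "improved metabolism is associated with shifts in skeletal muscle anabolic gene expression", and it goes on to catabolic genes and inflammation. Aim 5 links improved skeletal physiology to clinical indices, and confines this to HFrEF and HFpEF patients.

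Section 2.5 (Data Analysis) has two components. The first is a series of linear mixed models "with each of the skeletal muscle, platelet, gene expression, inflammatory, oxygen uptake and physical function related measures as the dependent variable", with participant group, "time point (baseline/4-week) and their interaction as fixed effects of interest". The second is one sentence, which plans Pearson/Spearman correlations to measure the strength of "associations between changes in measures of skeletal physiology and those of strength, gait speed and balance". It does not say whether these correlations are pooled over groups, run by group or adjusted for group, nor whether controls are included.

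Plasma nitrite is an endpoint in Section 2.4 but is not named among the mixed-model outcomes. Section 2.1 describes a non-randomized study of HFpEF, HFrEF and healthy controls.

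**The concern.** There are two gaps.

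First, an aim that claims an association needs an analysis that estimates one. A mixed model with respiration as the outcome shows whether mean respiration changed in each group. It does not show whether the subjects whose nitrite rose most were those whose respiration improved most. Followed as written, the plan would end with mean changes for most components of Aims 3 and 4 and no estimate of the links that those aims assert.

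Second, a plain correlation over mixed populations combines the association among similar subjects with any difference between group averages. If controls and HF subjects differ in both changes, a correlation appears even when the two are unrelated inside every group. Differences in opposite directions can cancel a real link. Since these correlations are meant to support a mechanism and to inform a larger trial, either error matters.

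**Working it through.** **The plan's own figures first.** Section 2.5 gives an SD of change of 32 (platelet respiration), a detectable within-group change of 32 and a detectable between-group difference of 42, at 80% power and two-sided α = 0.05. The documents give 30 subjects in total and no split; 10 per group is assumed.

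- Within group: noncentrality (32/32)·√10 = 3.16, 9 df, power 80.3%.
- Between groups: noncentrality (42/32)/√(2/10) = 1.3125/0.447 = 2.93, 18 df, power 79.3% (80.8% with pooled error, 27 df).

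Both reproduce, so the power statement is not in dispute and 10 per group is a reasonable assumption. The figure of 42 equals 42/32 = 1.31 SD.

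**Aims against analyses.**

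| Aim | Association claimed | Association analysis in Section 2.5 |
|---|---|---|
| 3 | plasma nitrite with muscle and platelet metabolism | none |
| 4 | metabolism with gene expression and inflammation | none |
| 5 | skeletal physiology with clinical indices, HF patients | correlations with strength, gait speed and balance |

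**Size of the pooling artefact.** Take unit within-group SD, zero within-group correlation, and both HF groups shifted by d SD from controls on both changes. The variance of the three group means is (2/9)d², so the pooled correlation is

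r = (2/9)d² / [1 + (2/9)d²].

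At d = 1.31 this is 0.383/1.383 = 0.28. Simulated rates (10 per group, Pearson, nominal 5%):

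| Subjects | Shift on the two changes (SD) | Mean unadjusted r | Significant, unadjusted | Significant, group-adjusted |
|---|---|---|---|---|
| All three groups, n = 30 | 0.5 and 0.5 | 0.05 | 6% | 5% |
| | 0.8 and 0.8 | 0.13 | 10% | 5% |
| | 1.0 and 1.0 | 0.19 | 16–17% | 5% |
| | 1.31 and 1.31 | 0.28 | 33% | 5% |
| | 1.31 and 0.5 | 0.12 | 10% | 5% |
| | 1.31 and 0 | 0.00 | 5% | 5% |
| HF only, n = 20 | HF groups alike | 0.00 | 5% | 5% |
| | HF groups 0.66 apart on both | 0.10 | 7% | 5% |

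Spearman is no safer: 33% at 1.31 SD on both.

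**The opposite error.** With a true within-group r of 0.5 and shifts of 1.31 SD in opposite directions, the pooled correlation is (0.5 − 0.383)/1.383 = 0.08. It is significant in 4% of runs, against 80% for the adjusted correlation.

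**Cost of adjusting.** Critical |r| = t/√(df + t²), with t the two-sided 5% point:

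- all groups, unadjusted, 28 df: 0.361
- all groups, adjusted, 26 df: 0.374
- HF only, adjusted, 17 df: 0.456
- one group of 10, 8 df: 0.632

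By Fisher's z, the r detectable with 80% power is tanh(2.80/√(n − k − 3)), with k the number of group terms: 0.49 for n = 30 unadjusted, 0.51 for n = 30 adjusted, and 0.79 for a single group of 10.

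**The case against.** The strongest reply is that Section 2.5 never says the groups will be pooled. Aim 5 concerns HF patients, and in that population the error rate is 5–7%. This stands: a reader might infer that the correlations disregard group by design, or that Aim 5 is tested at an inflated error rate, but the text is silent and supports neither. What remains is that the silence allows the pooled analysis.

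A reader might also infer that the plan expects a 1.31 SD group difference. It does not. The 42 is a minimum detectable difference, for platelet respiration only. Nothing in the documents supports a difference of that size in both a muscle measure and a functional one, and the artefact needs both. The greater HF response postulated in Section 2.2.2 is vasodilatory.

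Nor are Aims 3 and 4 wholly unanalysed. The mean changes in muscle, platelet, gene-expression and inflammatory measures are modelled; it is the association step that is absent.

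Finally, this is a pilot. The correlations are there to measure strength of association, and the plan weighs individual-subject plots and effect sizes beside p-values, holding that missing a finding is the costlier error. That lowers the stakes of a false positive. It does not supply the missing analyses, and the cancellation example shows that pooling can also cause missed findings.

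**Conclusion.** The omission for Aims 3 and 4 follows from the text and needs no assumption. For Aim 5, the defect is an unstated analysis set and no account of group. The consequence is conditional: from about 5% to 33% false positives if all three groups are pooled, depending on how far both changes differ between controls and HF subjects, and 5–7% in HF subjects alone. These rates assume 10 per group, equal SDs and no dose or age effects; the shifts are illustrative.

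One further inference should be resisted. Correlating change scores compares subjects with one another, with or without group adjustment, so the adjusted correlation does not isolate a within-subject mechanism. It removes differences between group averages only. The 20 or 40 mg tier is assigned by age and hypotension risk (synopsis, Study Design), so differences by tier or age can remain within a group.

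The change should be made, but it is not critical to a pilot.

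**What to change.** In Section 2.5:

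- Add the Aim 3 pairs (change in plasma nitrite with change in muscle and in platelet respiration) and the Aim 4 pairs (change in respiration with change in gene expression and in inflammatory markers) to the planned correlations.
- Use group-adjusted (partial) Pearson or Spearman correlations of the changes, report 95% CIs, and plot the points marked by group.
- Estimate Aim 5 in HF subjects, adjusted for HF type (17 df, critical |r| 0.456), with all three groups, adjusted (26 df, critical |r| 0.374), as a stated supplementary set.
- State that group adjustment does not remove differences by dose tier or age within a group.

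With all three groups, the adjustment costs 2 degrees of freedom: critical |r| rises from 0.361 to 0.374. Confining Aim 5 to its own population raises the threshold to 0.456 because only 20 subjects contribute, which is why the three-group estimate is worth keeping beside it. Separate correlations in each group of 10 would also avoid the artefact, but would need |r| above 0.632. Otherwise the cost is a few sentences and a little more analysis; no new data are needed.
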